8.6 Data Monitoring Committee

This study will institute a data monitoring committee (DMC) which will function independently of all other individuals associated with the conduct of this clinical trial, including the site investigators participating in the study. The DMC will be constituted prior to the randomization of the first patient. Further details on the function and responsibilities of the data monitoring committee will be outlined in the DMC charter.

8.7 Steering Committee

A Steering Committee (SC) will be established for this study. Further details on the functions and responsibilities will be outlined in the Steering Committee charter.

9 Data collection and management

9.1 Data confidentiality

Information about study subjects will be kept confidential and managed under the applicable laws and regulations. Those regulations require a signed subject authorization informing the subject of the following:

- What protected health information (PHI) will be collected from subjects in this study
- Who will have access to that information and why
- Who will use or disclose that information
- The rights of a research subject to revoke their authorization for use of their PHI.

In the event that a subject revokes authorization to collect or use PHI, the investigator, by regulation, retains the ability to use all information collected prior to the revocation of subject authorization. For subjects that have revoked authorization to collect or use PHI, attempts should be made to obtain permission to collect follow-up safety information (e.g. has the subject experienced any new or worsened AEs) at the end of their scheduled study period.

[figure not shown]
The data collection system for this study uses built-in security features to encrypt all data for transmission in both directions, preventing unauthorized access to confidential participant information. Access to the system will be controlled by a sequence of individually assigned user identification codes and passwords, made available only to authorized personnel who have completed prerequisite training.

Prior to entering key sensitive personally identifiable information (Subject Initials and exact Date of Birth), the system will prompt site to verify that this data is allowed to be collected. If the site indicates that country rules or ethics committee standards do not permit collection of these items, the system will not solicit Subject Initials. Year of birth will be solicited (in the place of exact date of birth) to establish that the subject satisfies protocol age requirements and to enable appropriate age-related normal ranges to be used in assessing laboratory test results.

9.2 Site monitoring

Before study initiation, at a site initiation visit or at an investigator's meeting, Novartis personnel (or designated CRO) will review the protocol and CRFs with the investigators and their staff. During the study, the field monitor will visit the site regularly to check the completeness of patient records, the accuracy of entries on the CRFs, the adherence to the protocol to Good Clinical Practice, the progress of enrollment, and to ensure that study treatment is being stored, dispensed, and accounted for according to specifications. Key study personnel must be available to assist the field monitor during these visits.

The investigator must maintain source documents for each patient in the study, consisting of case and visit notes (hospital or clinic medical records) containing demographic and medical information, laboratory data, electrocardiograms, and the results of any other tests or assessments. All information recorded on CRFs must be traceable to source documents in the patient's file. The investigator must also keep the original signed informed consent form (a signed copy is given to the patient).

The investigator must give the monitor access to all relevant source documents to confirm their consistency with the CRF entries. Novartis monitoring standards require full verification for the presence of informed consent, adherence to the inclusion/exclusion criteria and documentation of SAEs. Additional checks of the consistency of the source data with the CRFs are performed according to the study-specific monitoring plan.

9.3 Data collection

For studies using Electronic Data Capture (EDC), the designated investigator staff will enter the data required by the protocol into the Electronic Case Report Forms (eCRF). The eCRFs have been built using fully validated secure web-enabled software that conforms to 21 CFR Part 11 requirements. Investigator site staff will not be given access to the EDC system until they have been trained. Automatic validation programs check for data discrepancies in the eCRFs and, allow modification or verification of the entered data by the investigator staff.

The Principal Investigator is responsible for assuring that the data entered into eCRF is complete, accurate, and that entry and updates are performed in a timely manner.

9.4 Database management and quality control

[figure not shown]
For studies using eCRFs, Novartis personnel (or designated CRO) will review the data entered by investigational staff for completeness and accuracy. Electronic data queries stating the nature of the problem and requesting clarification will be created for discrepancies and missing values and sent to the investigational site via the EDC system. Designated investigator site staff are required to respond promptly to queries and to make any necessary changes to the data.

Concomitant treatments and prior medications entered into the database will be coded using the WHO Drug Reference List, which employs the Anatomical Therapeutic Chemical classification system. Medical history/current medical conditions and adverse events will be coded using the Medical dictionary for regulatory activities (MedDRA) terminology.

Samples and/or data that will be processed centrally will have results sent electronically to Novartis (or a designated CRO).

Randomization codes and data about all study treatments dispensed to the patient and all IRT assigned dosage changes will be tracked using an Interactive Response Technology. The system will be supplied by a vendor(s), who will also manage the database. The data will be sent electronically to Novartis personnel (or designated CRO).

At the conclusion of the study, the occurrence of any emergency code breaks will be determined after return of all code break reports and unused drug supplies to Novartis personnel (or designated CRO). The occurrence of any protocol violations will be determined. After these actions have been completed and the data has been verified to be complete and accurate, the database will be declared locked and the treatment codes will be unblinded and made available for data analysis. Authorization is required prior to making any database changes to locked data, by joint written agreement between the Global Head of Biostatistics and Data Management and the Global Head of Clinical Development.

For EDC studies, after database lock, the investigator will receive a CD-ROM or paper copies of the patient data for archiving at the investigational site.

10 Statistical methods and data analysis

The data from all participating centers in this protocol will be combined. The interim analysis will be performed once 45 PFS-1 events have been documented. The primary analysis of study data will be conducted when approximately 90 PFS-1 events have been documented. This data will be summarized in the primary Clinical Study Report (CSR). All available data from all patients up to this cutoff date will be analyzed.

10.1 Analysis sets

10.1.1 Full Analysis Set

The Full Analysis Set (FAS) comprises all patients to whom study treatment has been assigned by randomization. According to the intent to treat principle, patients will be analyzed according to the treatment they have been assigned to during the randomization procedure.

10.1.2 Safety Set

The Safety Set includes all patients who received at least one dose of study medication, where treatment received is defined as the randomized treatment if the patient takes at least one dose of that treatment or the first treatment received if the randomized treatment is never received.

10.1.3 Per-Protocol Set

The Per-Protocol Set (PPS) consists of a subset of the patients in the FAS who have at least one post-baseline assessment for PFS and no major protocol deviations.

All major protocol deviations leading to exclusion from the PPS will be detailed in the analysis plan.

[figure not shown]
10.1.4 Pharmacokinetic analysis set

The pharmacokinetic Analysis Set (PAS) consists of all patients set who have received at least one dose of ruxolitinib and provided evaluable pharmacokinetic (PK) data.

Evaluable PK data must fulfill the following criteria:

1. Post-dose data must not be associated with a vomiting event within 4 hours of ruxolitinib dosing
2. Pre-dose sample must not be associated with vomiting within 4 hours of last dose.
3. Post-dose PK samples must be collected within the time window indicated in the PK collection log.

The PAS will be used for the Population PK analysis.

10.2 Patient demographics/other baseline characteristics

Demographic and other baseline data (including disease characteristics) will be summarized descriptively by treatment group for the FAS.

Categorical data will be presented as frequencies and percentages. For continuous data, mean, standard deviation, median, 25th and 75th percentiles, minimum, and maximum will be presented.

10.3 Treatments (study treatment, concomitant therapies, compliance)

The safety set will be used for the analyses below.

The actual dose and duration of ruxolitinib and placebo treatment as well as the dose intensity (computed as the ratio of total dose received and actual treatment duration) and the relative dose intensity (computed as the ratio of dose intensity and planned dose intensity), will be listed and summarized by treatment group. Dose reductions and dose interruptions (including the reasons for these) will be listed and summarized by treatment group.

Concomitant medications including prohibited medications, and significant non-drug therapies prior to and after the start of the study treatment will be summarized for all patients and by treatment group.

Duration of follow up will be summarized descriptively by treatment group.

10.4 Primary objective

The primary objective for this study is to evaluate the effect of ruxolitinib in delaying progression of MF from early disease to more advanced disease stages.

10.4.1 Variable

The primary endpoint is **progression free survival (PFS-1) in Treatment Period 1**. It is defined as the time from date of randomization until earliest time for one of the following events:

- Progressive splenomegaly as assessed by doubling of spleen volume (by MRI/CT); in addition to an absolute spleen volume of greater than 450 cm³.
- Circulating peripheral blast counts > 10% (requires confirmation after 8 weeks)
- Leukemic transformation defined by an increase in peripheral blood blast percentage to $\geq 20\%$ that is sustained for at least 8 weeks or a bone marrow blast count of $\geq 20\%$
- Hb < 10g/dl with an absolute decrease of at least 3 g/dl from baseline levels (requires confirmation following 2 week of dose interruption/reductions to ensure this is not drug induced cytopenia. In case of Hb stabilizing following dose modification within the 2 weeks, study drug can be re-escalated based on investigators discretion. See section 6.3 for guidance on dosing modifications)
- WBC counts > 25 x 10³/ μ L

- Confirmed MF-7 score of ≥ 30 in addition to an individual symptom score of ≥ 7 in at least one non-splenomegaly related symptom, i.e., tiredness, night sweats, itching (pruritus), bone pain (diffuse not joint pain or arthritis). (Confirmed on two consecutive weeks)
- Death from any cause

As the proposed study intends to investigate the benefit of ruxolitinib in delaying the emergence of MF associated symptoms, MF-7 is expected to objectively evaluate disease progression based on the worsening of symptoms through symptom scores. A clinically relevant threshold of ≥ 30 was set to capture the time point when the patient begins experiencing more symptomatic disease (disease progression) reflected by a minimum of doubling in the baseline MF-7 scores. Additionally, progression by symptom will also require an individual score of ≥ 7 in at least one non-splenomegaly related symptom, i.e., tiredness, night sweats, itching (pruritus), bone pain (diffuse not joint pain or arthritis).

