1.2.1.2.3 Summary of Clinical safety data

In the randomized period of the two pivotal studies in MF, COMFORT-I and COMFORT-II discontinuation due to adverse events, regardless of causality was observed in 11.3% of patients. The most frequently reported adverse drug reactions were thrombocytopenia and anemia. Hematological adverse reactions (any Common Terminology Criteria for Adverse Events [CTCAE] Grade) included anemia (82.4%), thrombocytopenia (69.8%) and neutropenia (16.6 %). Anemia, thrombocytopenia and neutropenia are dose related effects. The three most frequent non-hematological adverse reactions were bruising (21.6%), dizziness (15.3%) and headache (14.0%). The three most frequent non-hematological laboratory abnormalities were raised alanine aminotransferase (27.2%), raised aspartate aminotransferase (18.6%) and hypercholesterolemia (16.9%).

Long-term follow-up in patients with MF in the phase I/II study INCB 18424-251 and the COMFORT studies has shown that as expected, the numbers and proportions of adverse events (AEs) and serious adverse events (SAEs) have increased; however, no new safety signals have emerged. Additionally in patients with MF, the dose optimization strategy of dose reduction and occasional dose interruption for thrombocytopenia was successful in maintaining patients on therapy with only one patient on the ruxolitinib arm of each study discontinuing for thrombocytopenia; platelet transfusions occurred with low frequency, comparable to the control arms in the Phase III studies.

[figure not shown]
Overall, the safety profile of ruxolitinib in the PV population treated with ruxolitinib is generally consistent with what was observed in the MF population. Ruxolitinib was generally well tolerated in patients with PV and only a small proportion of patients discontinued ruxolitinib due to AEs (3.6%). Most of the AEs have been managed by dose adjustments. Hematological toxicities were less frequent and less severe in patients with PV as compared to those observed in patients with MF.

No new safety signals emerged from a study in pancreatic cancer in combination with capecitabine.

The AE profile of ruxolitinib has also been assessed in 198 healthy volunteers, subjects with various degrees of renal (n=32) or hepatic (n=24) impairment, and in patients with RA (n=59) receiving ruxolitinib: AEs were, in general, mild and resolved without interventions.

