5.2 Inclusion criteria

Patients eligible for inclusion in this study have to meet **all** of the following criteria at screening:

Written informed consent must be obtained prior to any screening procedures.

1. Male or Female aged 18 or over.
2. Confirmed diagnosis of MF with bone marrow fibrosis of at least Grade 1 ([Appendix 2](#)); irrespective of JAK2 mutational status.

3. Patients with at least one mutation in one of the five HMR genes (ASXL1, EZH2, SRSF2 and IDH1/2).
4. Patients with non-palpable spleen or spleen palpable ≤ 5 cm from the left costal margin to the point of greatest splenic protrusion.
5. Patients with MF-7 score of ≤ 15 , with each individual symptom score of ≤ 3 .
6. Patients with a peripheral blood blast count percentage of $< 1\%$.
7. Patients with Hemoglobin $> 10\text{g/dL}$.
8. Patients with platelet counts $\geq 75,000/\mu\text{L}$.
9. Patients with Absolute neutrophil count (ANC) $\geq 1000/\mu\text{L}$.
10. Patients with WBC $\leq 15 \times 10^3/\mu\text{L}$.
11. Patients with an Eastern Cooperative Oncology Group (ECOG) performance status of 0, 1, or 2.

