6.3 Dose modifications

6.3.1 Dose modification and dose delay

6.3.1.1 Dose modification for hematologic toxicity

Treatment Period 1

Dose reductions or interruptions for hematological changes are permitted in order to allow the patient to continue on the study treatment. The maximum allowed doses for different ranges of cytopenia is described in [Table 6-4](#). The objective of the dose adjustment rules is to optimize treatment response for each individual patient while avoiding significant cytopenia. Dosing may be restarted or increased following recovery of the hematologic parameter(s) to acceptable levels. Any patient requiring dose interruption continuously for more than 4 weeks

due to decreases in ANC or platelet (PLT) counts must be permanently discontinued from treatment. Hb levels decreasing below 8g/dL with an absolute drop of 3g/dL from baseline, will constitute a marker of progressive MF disease, if Hb levels fail to recover \geq 8g/dL following treatment interruption for two consecutive weeks. Such patients must permanently discontinue study treatment.

Table 6-4 Dose reductions and interruptions due to hematological changes – Treatment Period 1

Current Hb (g/dL)	Maximum allowable dose
< 8	Interrupt dosing (HOLD)
8 to < 10	Reduce total daily dose to 5 mg BID
Current PLT ($\times 10^9/L$)	
< 50	Interrupt dosing (HOLD)
50 to < 75	Reduce total daily dose to 5 mg BID
Current ANC ($\times 10^9/L$)	
< 0.5	Interrupt dosing (HOLD)
0.5 to < 0.75	Reduce total daily dose to 5 mg BID

All dose changes must be recorded on the Dosage Administration Record CRF.

Patients whose dose has been interrupted for more than 4 weeks for any reason are recommended to be permanently discontinued from study treatment.

Treatment Period 2

Dose reductions and interruptions for ruxolitinib treatment during ‘Treatment Period 2’ can be performed in accordance with the local label requirements. In countries where ruxolitinib is not currently approved, treatment should be discontinued for platelet counts less than $50 \times 10^9/L$ or absolute neutrophil counts less than $0.5 \times 10^9/L$. After recovery of blood counts above these levels, dosing may be re-started at 5 mg twice daily and gradually increased based on careful monitoring of complete blood cell count, including a white blood cell count differential.

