10.4.4 Supportive analyses

A summary of first progression (PFS-1) events will be tabulated by treatment group.

A subgroup analysis of PFS will be performed by IPSS risk group, type & number of HMR mutations, presence of palpable splenomegaly and/or active symptoms as determined by MF-7.

The analysis of PFS will be repeated for per protocol set.

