10.4.5 Sensitivity analyses

If progression event occurs between two scheduled assessments then a date of next schedule assessment will be used as end date for PFS and the outcome will be an event.

If a progression event occurs after two or more missing assessments then date of next scheduled assessment will be used as end date for PFS and the outcome will be an event.

If a patient permanent discontinues study treatment for reason other than disease progression and progression event occurs between permanent discontinuation and start of new anti-neoplastic treatment then the actual date of event will be used and PFS will not be censored.

An alternative definition of PFS excluding MF-7 from progression will be performed.

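### The PFS-1 hemoglobin criterion can be confirmed while the patient is still taking reduced-dose ruxolitinib, and no planned analysis estimates the PFS effect without hemoglobin events.

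*Protocol*

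**What the plan says.** **The criterion.** Protocol 10.4.1 lists Hb below 10 g/dL with a fall of at least 3 g/dL from baseline as a PFS-1 event. It "requires confirmation following 2 week of dose interruption/reductions to ensure this is not drug induced cytopenia", and the reader is sent to section 6.3 for dosing.

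**The dosing table.** Table 6-4 in 6.3.1.1 sets maximum allowable doses in Treatment Period 1. Below 8 g/dL dosing is held. At 8 to <10 g/dL the entry is "Reduce total daily dose to 5 mg BID".

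**A second Hb rule.** The text above that table says "Hb levels decreasing below 8g/dL with an absolute drop of 3g/dL from baseline, will constitute a marker of progressive MF disease" if Hb does not recover to 8 g/dL or more after two consecutive weeks of interruption. Both the threshold and the confirmation step differ from 10.4.1.

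**The toxicity.** Section 1.2.1.2.3 reports anemia of any grade in 82.4% of patients across the two pivotal MF studies and adds: "Anemia, thrombocytopenia and neutropenia are dose related effects".

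**Planned analyses.** The sensitivity analyses in 10.4.5 vary event dating, missed assessments and events after discontinuation. The single change of definition is: "An alternative definition of PFS excluding MF-7 from progression will be performed". Section 10.4.4 adds: "A summary of first progression (PFS-1) events will be tabulated by treatment group".

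**The concern.** The confirmation step exists to separate drug-induced anemia from disease progression. If the confirming sample is taken on a reduced dose of a drug whose anemia is dose related, a persistently low value does not rule the drug out. Only the ruxolitinib arm can have such events, so any that are counted push the PFS-1 hazard ratio toward 1, lower power and make a futility crossing more likely. A disappointing result would then be hard to read: the drug may fail to delay myelofibrosis, or it may delay it while lowering hemoglobin. The plan re-estimates PFS without the symptom component but not without the component most exposed to the drug's own toxicity. Time to progression does not help, because it removes only death and keeps the Hb criterion.

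**Working it through.** **1. Who can be confirmed on drug.** The trigger needs Hb <10 g/dL and a fall of at least 3 g/dL. Entry requires Hb above 10 g/dL (section 5.2), with no upper limit.
- Baseline 10.5: trigger at or below 10.5 − 3 = 7.5, so Table 6-4 requires a hold.
- Baseline 10.9: at or below 7.9, hold.
- Baseline 11.0: at or below 8.0, so the 8 to <10 band is just reachable.
- Baseline 12.0: at or below 9.0, band reachable.
- Baseline 13.0 or more: any value below 10, band reachable.

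The route is open from a baseline of about 11 g/dL, and only when the value stays at 8 or above.

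**2. The plan's own figures.** Inputs from 10.7 and 10.8: HR 0.50, medians 50 and 100 months, one-sided 2.5%, 1:1 allocation, 90 events, futility bound z = 0.388 at 45 events.
- Schoenfeld events: 4 × (1.960 + 1.282)² / (ln 0.50)² = 88, against 90 stated.
- Power at 90 events: Φ(0.693 × √(90/4) − 1.96) = Φ(1.33) = 91%.
- Futility crossing at HR 0.50: Φ(0.388 − 0.693 × √(45/4)) = Φ(−1.94) = 2.6%, against 3% stated.

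The design reproduces.

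**3. Adding false Hb events on ruxolitinib, constant hazard.** The documents give no rate, so the cumulative 36-month risk q is an assumption. Monthly hazards: placebo ln 2/50 = 0.01386; ruxolitinib ln 2/100 = 0.00693; false Hb −ln(1 − q)/36. Observed HR = (0.00693 + false)/0.01386. For q = 5% the false hazard is 0.00142 and HR = 0.00836/0.01386 = 0.60. Power is then Φ(0.506 × 4.743 − 1.96) = Φ(0.44) = 67%, and futility crossing is Φ(0.388 − 0.506 × 3.354) = Φ(−1.31) = 10%.

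| q by month 36 (assumed) | HR | Power at 90 events | Futility crossing |
|---|---|---|---|
| 0% | 0.50 | 91% | 3% |
| 2% | 0.54 | 83% | 5% |
| 5% | 0.60 | 67% | 10% |
| 10% | 0.71 | 37% | 23% |

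The largest HR that is significant at 90 events is exp(−1.96 × 2/√90) = 0.66, reached at q of roughly 7.5%.

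**4. The same, with all false events early.** Simulated trials (320 patients, 13 per month, 15% dropout by month 48, exponential PFS), with false events spread uniformly over months 1 to 12:

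| Patients with a false event (assumed) | Mean HR | Power, futility ignored | Futility crossing |
|---|---|---|---|
| 2% | 0.56 | 81% | 9% |
| 5% | 0.63 | 58% | 23% |
| 8% | 0.73 | 32% | 47% |

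Repeat runs agree within about 3 percentage points. The documents do not support early timing over a constant rate, so steps 3 and 4 are two cases of an unknown.

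**5. What an analysis without Hb would retain.** It removes every Hb event, genuine or not. Let s be the share of genuine events that are Hb events (assumed). Approximate events left at the same cut-off = 90 × (1 − s) × (0.01386 + 0.00693)/(0.01386 + 0.00693 + false). With q = 5% the ratio is 0.936, giving 84 events at s = 0 and 59 at s = 30%. The HR returns to 0.50 if the effect on the remaining components is 0.50. Power is 89% and 76% respectively.

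**The case against.** **A reader might infer that no planned analysis would show the problem.** The documents do not support that. PFS-1 events are tabulated by arm (10.4.4), and one criterion is recorded per patient (7.2.1.1). Dose reductions and interruptions are summarized by arm with reasons (10.3). Time to progressive splenomegaly and time to symptomatic progression are analysed separately and contain no Hb component (10.5.1), and hematology shift tables are planned by arm (10.5.2.3). Many Hb events on ruxolitinib beside favourable spleen and symptom results would be visible. What these outputs do not give is a PFS effect without Hb events. The spleen and symptom analyses each cover one component and omit blasts, leukemic transformation, WBC and death. Section 10.4.4 does not say that its table is by criterion.

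**Table 6-4 sets a ceiling.** Interruption at 8 to <10 g/dL is not forbidden, and the rule in 6.3.1.1 relies on interruption. That stands: confirmation on drug is permitted, not required.

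**The 82.4% figure cannot serve as the false-event rate.** It is any-grade anemia in more advanced disease, and section 2.3 says hematological events were fewer and milder at 10 mg BID than at 15 mg BID. It shows only that the mechanism is plausible.

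**The error is conservative.** It works against ruxolitinib, so it does not favour a false claim of benefit. The futility bound is non-binding, and details of the interim analysis are left to a DMC charter outside these documents, so nothing can be said to be missing from what the committee receives.

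**Conclusion.** The point holds with limits. For patients with baseline Hb of about 11 g/dL or more who trigger at 8 to <10 g/dL, the confirmation step in 10.4.1 can be met on active drug, so it does not fully do what it is stated to do. Sections 10.4.1 and 6.3.1.1 also disagree on which Hb fall is progression and how it is confirmed. An excess of Hb events could be seen, but no planned analysis gives the PFS effect without them.

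The size cannot be known from the documents. At an assumed 5% false-event rate the HR moves from 0.50 to about 0.60 or 0.63, power from 91% to about 67% or 58%, and futility crossing from 3% to about 10% or 23%, depending on timing. Smaller rates matter less: 2% leaves power at 83% or 81%. All these figures assume a true HR of 0.50 and false events in the ruxolitinib arm only.

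A reader might also infer that the trial's report is affected. It is not. SAP sections 1.1, 2.5 and 2.7 drop the interim analysis, the derivation of PFS and the secondary efficacy analyses after early termination, so the point concerns the protocol's PFS-1 plan.

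**What to change.** 1. Reconcile the Hb progression rules in sections 6.3.1.1 and 10.4.1, so that one definition and one confirmation step apply throughout.
2. Add to 10.4.5 a supportive alternative definition of PFS that excludes the Hb criterion, reported with a log-rank test, hazard ratio and 95% confidence interval.
3. State in 10.4.4 that the PFS-1 event table is by criterion and arm, with Hb events split by whether confirmation was on interruption or on a reduced dose.

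The analyses in items 2 and 3 leave the primary definition and the dose rules as they are.

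**Cost.** One extra analysis and a fuller table, from data already collected. The supportive analysis also discards genuine Hb progressions and censors those patients, because assessment of most other criteria stops at progression. Events and power fall, to about 84 to 59 events and 89% to 76% power in the assumed 5% case, and the censoring may be informative. It should be read beside the primary result, not in place of it.
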